#### 4.1.1 Screening

Pediatric patients for both cohorts will be screened for eligibility during the 28 days immediately prior to starting study treatment on Day 1. During this time, the inclusion and exclusion criteria will be assessed and all screening procedures will be performed. Results of all screening evaluations must be reviewed by the investigator or his/her designee prior to enrollment of each patient into the study to ensure all criteria have been met.

Eligible patients may only be included in the study after the patient or parental/legal guardian provides written (witnessed, where required by law or regulation) informed consent. In cases where the patient's representative gives consent, the patient should be informed about the study to the extent possible given his/her understanding. If the patient is capable of doing so, he/she should indicate assent by personally signing and dating the written informed consent document or a separate assent form.

As part of the screening, all patients must have available tumor samples (either formalin-fixed, paraffin-embedded [FFPE] blocks or slides) for central confirmation of *BRAF* V600 mutation (HGG and LGG), and for patients enrolled into the HGG cohort, for independent confirmation of HGG histopathology by an independent neuropathologist. The sample should be the best representation of the tumor and submitted for central confirmation approximately within one month of enrollment onto the study. Eligibility will be assessed based on local results of histology and *BRAF* V600 mutation.

Central confirmation of baseline measurable disease by an independent radiologist will be required before enrollment.

Following the completion of screening procedures and verifying patient eligibility based on assessments, the patient will be enrolled via the Interactive Response Technology (IRT) system. Please refer to and comply with detailed guidelines in the IRT manual. IRT systems will confirm the inclusion of eligible patients.

#### 4.1.2 Treatment

The study treatment phase begins on Day 1 with the first administration of study treatment. In the HGG cohort, all patients will receive dabrafenib in combination with trametinib. In the LGG cohort, patients will be randomized 2:1 to receive dabrafenib in combination with trametinib or carboplatin with vincristine.

All patients who receive dabrafenib with trametinib will take dabrafenib twice daily and trametinib once daily until no longer receiving clinical benefit as determined by the investigator, disease progression, death, unacceptable toxicity that precludes further treatment, start of new anticancer therapy, or study is terminated by Sponsor.

Patients enrolled into the LGG cohort and randomized in the control arm will be administered carboplatin with vincristine, according to the regimen defined in Section 6.1.2. Treatment should continue for the prescribed number of cycles, as tolerated, or until unacceptable toxicity, start of a new anti-neoplastic therapy, discontinuation at the discretion of the investigator or patient/legal guardian, lost to follow-up, death, study is terminated by the sponsor or until disease progression. Patients randomized to the control arm are expected to follow protocol specified evaluations according to Table 7-3, including efficacy and safety assessments.

Patients in both cohorts will be assessed at screening (within 28 days before initiation of study treatment) and every 8 weeks for the first year on treatment, and every 16 weeks thereafter for efficacy using RANO criteria. All radiological scans will be collected for independent central review.

In the HGG cohort, clinical response will be monitored during the study to enable early stopping for futility if sufficient clinical activity is not demonstrated. After the first 16 patients have been

enrolled, have completed at least 20 weeks of treatment or have discontinued treatment earlier, an interim analysis will be conducted in order to determine whether the futility criteria have been met.

Safety assessments (collection of AEs, concomitant medications, laboratory parameters, dermatologic skin evaluations, and ophthalmologic exams) will be conducted on a continuous basis during the treatment phase according to Table 7-1, Table 7-2 for LGG crossover patients or Table 7-3.

#### 4.1.2.1 Treatment after Progression of Disease

Patients receiving dabrafenib with trametinib are permitted to continue treatment beyond investigator-assessed, RANO-defined PD, as long as they meet the following criteria:

- Investigator assessed clear evidence of clinical benefit
- Tolerance of study treatment
- Continuation of study treatment is in the best interest of the patient as determined by the Investigator
- Patient/legal guardian is willing to continue on the study and sign Informed Consent for treatment beyond progression

If the Principal Investigator determines that all above criteria are met, the patient may continue dabrafenib with trametinib treatment on study and follow all study related procedures, including tumor assessments, as scheduled in Table 7-1. After each tumor assessment, the Principal investigator must confirm if the patient is still benefitting from study treatment, and document this in patient medical records and the eCRF.

#### 4.1.2.2 Crossover and Continuation of Treatment (LGG Cohort)

For the LGG cohort, patients randomized to the carboplatin with vincristine treatment arm will be allowed to crossover to receive dabrafenib in combination with trametinib treatment after centrally confirmed and RANO-defined disease progression. Patients who cross over are expected to continue to undergo protocol specified evaluations according to Table 7-2, including efficacy and safety assessments.

LGG patients who crossover to receive dabrafenib in combination with trametinib must continue to meet the inclusion criteria for cardiac function, be willing to follow all contraception guidance, and cannot meet the exclusion criteria for allergy to dabrafenib, trametinib, or their excipients. Measurable disease is not mandatory but a new baseline tumor evaluation must be established within 28 days of starting dabrafenib in combination with trametinib crossover treatment. Day 1 of crossover therapy must occur within 90 days from the date of the first centrally confirmed progression. After the final PFS analysis and assuming significant favorable ORR and favorable PFS for the experimental therapy, patients randomized to carboplatin plus vincristine arm with persistent stable disease and deemed suitable for further systemic therapy for their disease may be allowed to crossover to receive dabrafenib in combination with trametinib.

PRO, taste questionnaires and pharmacokinetic samples will not be obtained on those patients who cross over to receive dabrafenib plus trametinib therapy.

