## **Summary of previous amendment**

## **Amendment 4 (11-Mar-2019)**

As of 28-Feb-2019, fifteen (15) patients have been enrolled and treated in the HGG cohort of CDRB436G2201 and fourteen (14) patients have been randomized in the LGG cohort of CDRB436G2201.

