#### **Amendment rationale**

The purpose of this amendment is to add an additional interim analysis of key safety and pharmacokinetics (PK) data of the adolescent patients (ages  $\ge 12$  to <18 years) in the HGG cohort to support a health authority request in the 1st half of 2019 for data in adolescent patients.

In addition, exclusion criteria #18 was added to exclude patients with history or current evidence of retinal vein occlusion and central serous retinopathy. This exclusion criteria is standard language for all studies with trametinib and was inadvertently omitted from previous versions of CDRB436G2201.

Also, optional cerebrospinal fluid (CSF) collection was removed. Based on experience to date, CSF samples are expected to be very limited (1/30 patients provide a sample). Hence, the value of the analyses is limited.

Other clarifications and corrections are also applied throughout the protocol.

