LGG patients receiving carboplatin with vincristine treatment will follow the regimen in Section 6.1.2 in conjunction with institutional practice. Duration of treatment should continue for the prescribed number of cycles as tolerated, or until unacceptable toxicity, start of a new anti-neoplastic therapy, discontinuation at the discretion of the investigator or patient/legal guardian, lost to follow-up, death, study termination by the sponsor, or until disease progression. See Section 6.3.1.16 for dose modifications and management guidelines or carboplatin with vincristine. Patients randomized to the carboplatin with vincristine treatment arm will only be allowed to cross over to receive dabrafenib in combination with trametinib after centrally confirmed RANO-defined disease progression. Crossover will be allowed during the treatment period or the post-treatment period.

LGG patients on dabrafenib with trametinib treatment may continue to receive the assigned study treatment until disease progression by RANO criteria or loss of clinical benefit as determined by the investigator, unacceptable toxicity, start of a new anti-neoplastic therapy, discontinuation at the discretion of the investigator or patient/legal guardian, lost to follow-up, death, or study termination by the sponsor.

LGG patients receiving dabrafenib with trametinib who have disease progression by RANO criteria may continue study treatment if the investigator determines that patient has clear evidence of clinical benefit from study treatment, continuing study treatment may be in the best interest for the patient, and the patient/legal guardian is willing to continue on study treatment and sign the Informed Consent for treatment beyond progression. The decision to continue study treatment after PD must be documented in the patient records and eCRF after every tumor

evaluation. In this case, the patient will continue assessments as defined in Section 7. An End

of Treatment visit will be performed when patients permanently discontinue study treatment.

Patients who discontinue dabrafenib with trametinib treatment or complete carboplatin with vincristine treatment without disease progression by RANO criteria will continue tumor assessment as part of the post treatment follow-up outlined in Section 7 until central independently confirmed disease progression by RANO criteria or death irrespective of start of new anti-neoplastic therapy.

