  - Female sterilization (have had surgical bilateral oophorectomy with or without hysterectomy), total hysterectomy, or bilateral tubal ligation or tubal occlusion at least six weeks before taking study treatment. In case of oophorectomy alone, only when the reproductive status of the woman has been confirmed by follow up hormone level assessment is she considered not of child bearing potential.

- Male sterilization (at least 6 months prior to screening). For female patients on the study, the vasectomized male partner should be the sole partner for that patient.
- Placement of a hormonal or non-hormonal intrauterine device (IUD) or intrauterine system (IUS) with a documented failure rate of less than 1% per year.

**Note:** Oral contraceptives are not permitted as a method of contraception due to potential drugdrug interactions with dabrafenib.

- 15. Pregnant females as determined by positive human chorionic gonadotropin (hCG) test at screening or prior to dosing.
- 16. Lactating females who are actively breast feeding.
- 17. Sexually active males (including those that have had a vasectomy) unless they use a condom during intercourse while on study and for 16 weeks after stopping study treatment, and agree not to father a child during this period.
- 18. A history or current evidence of retina vein occlusion (RVO) or central serous retinopathy.

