# 6.3.1.4 Dose modification and management guideline for visual changes suspected to be related to dabrafenib and/or trametinib treatment

Episodes of visual changes have been observed in patients receiving trametinib, dabrafenib, and combination therapy. An ophthalmologist is to be consulted if changes in vision develop. However, if the visual changes are clearly unrelated to study treatment (e.g., allergic conjunctivitis), then monitor closely as it may be reasonable to defer ophthalmic examination.

Special attention should be given to retinal findings (e.g., retinal pigment epithelial detachment (RPED) or retinovascular abnormalities (i.e., branch or central retinal vein occlusions (RVO). Treatment emergent cases of RVO and RPED are to be reported as SAEs.

Guidelines for dose modifications and management for visual changes and/or ophthalmic examination findings considered to be related to study treatment are provided in Table 6-19 and Table 6-20.

Treatment with dabrafenib has been associated with the development of uveitis, including iritis. Monitor patients for visual signs and symptoms (such as, change in vision, photophobia and eye pain) during therapy. Guidelines for dose modifications and management for uveitis, including iritis considered to be related to study treatment are provided in Table 6-21.

Table 6-19 Mandatory dose modification and recommended clinical management for visual changes and/or ophthalmic examination findings suspected to be related to trametinib treatment

| Visual changes (Eye disorders – Other, CTCAE Version 4.03, retinal, and similar)   |  |  |  |
|--|--|--|--|
| Grade  | Recommended adverse event management guidelines                            | Mandatory dose modification requirements   |  |
| Grade 1  If visual changes are clearly unrelated to study treatment (e.g. allergic conjunctivitis), monitor closely but ophthalmic examination is not required | Initiate local therapy and consult ophthalmologist within 7 days of onset. | 
 
If dilated fundus examination cannot be performed within 7 days of onset, interrupt trametinib until RPED and RVO can be excluded by retina specialist/ophthalmologist. Continue dabrafenib.
 
If RPED and RVO excluded, continue (or restart) trametinib at same dose level
 
If RPED suspected or diagnosed: see RPED dose modification Table 6-20; report as SAE if diagnosed.
 
If RVO diagnosed: Permanently discontinue trametinib and report as SAE.
 
 |  |

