| Visual changes (Eye | e disorders – Other, CTCAE Version 4                           | .03, retinal, and similar)  |  |  |  |  |  |  |
|---------------------|--|---|--|--|--|--|--|--|
| Grade               | Recommended adverse event management guidelines                | Mandatory dose modification requirements  |  |  |  |  |  |  |
| Grade 2 and Grade 3 | Initiate local therapy and consult ophthalmologist immediately | Interrupt trametinib. Dabrafenib may be continued at the current dose.                      |  |  |  |  |  |  |
|                     |  | If RPED and RVO excluded, restart trametinib at same dose level.                            |  |  |  |  |  |  |
|                     |  | If RPED diagnosed, see RPED dose modification in Table 6-20; report as SAE.                 |  |  |  |  |  |  |
|                     |  | If RVO diagnosed: Permanently discontinue trametinib and report as SAE.                     |  |  |  |  |  |  |
| Grade 4             | Initiate local therapy and consult ophthalmologist immediately | Interrupt trametinib. Dabrafenib may be continued at the same dose.                         |  |  |  |  |  |  |
|                     |  | If RPED and RVO excluded, consider restarting trametinib at the same or reduced dose level. |  |  |  |  |  |  |
|                     |  | If RVO diagnosed, permanently discontinue trametinib and report as SAE.                     |  |  |  |  |  |  |

Table 6-20 Mandatory dose modification and recommended clinical management for retinal pigment epithelial detachments (RPED) suspected to be related to trametinib treatment

| Re | Retinal pigment epithelial detachments (RPED)                                 |   |  |  |  |  |  |  |  |  |  |  |  |  |  |
|----|---|---|--|--|--|--|--|--|--|--|--|--|--|--|--|
| Gr | ade   | Recommended adverse event management guidelines | Mandatory dose modification requirements   |  |  |  |  |  |  |  |  |  |  |  |  |
| •  | Grade 1 (Asymptomatic; clinical or diagnostic observations only)              | If RPED worsens follow instructions below.      | Continue treatment with retinal evaluation monthly until resolution.   |  |  |  |  |  |  |  |  |  |  |  |  |
| •  | Grade 2-3 RPED (Symptomatic with mild to moderate decrease in visual acuity). | Retinal evaluation monthly.                     | 
 
Interrupt trametinib.
 
If improved to ≤ Grade 1, restart trametinib at a lower dose.
 
 |  |  |  |  |  |  |  |  |  |  |  |  |

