| Adverse events               | D        | 8.1              |               | X – C | X – Continuous |         |                  |         |         |                        |       |        |      |       |        |  |   |  |                                   |
| Dermatological
Evaluation | D        | 7.2.2.6          |               |       |                |         | X                |         | /lonthl |                        |       | ualifi | ed p | hysio | cian a | ssessment                                      | X – At EOT months after dose of stude treatment of of new antire therapy initial. | r the last
dy
until start
leoplastic                      |                                   |
| ECG                          | D        | 7.2.2.1
0.1   | Х             |       |                |         |                  | Х       |         | Х                      |       | Х      |      | Х     |        | Х  | Х   |  |                                   |
| Cardiac imaging/
ECHO     | D        | 7.2.2.1
0.2   | Х             |       |                |         |                  | Х       |         | Х                      |       | Х      |      | Х     |        | Х  | Х   |  |                                   |
| Ophthalmic examination       | D        | 7.2.2.7          |               |       |                |         |                  | Х       |         | Х                      |       | Х      |      | Х     |        | Х  | Х   |  |                                   |
| Study drug administrat       | ion      |                  |               |       |                | •       | •                | •       |         | •                      |       | •      |      |       | •      |  |   | •  |                                   |
| DRB436 administration        | D        | 6.1              |               | X - C | ontin          | uous    | b.i.d da         | aily do | sing    |                        |       |        |      |       |        |  |   |  |                                   |
| TMT212 administration        | D        | 6.1              |               | X – C | Contir         | nuous   | q.d. da          | aily do | sing    |                        |       |        |      |       |        |  |   |  |                                   |

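### Crossover to trametinib in the LGG cohort does not re-apply retinal exclusion criterion 18 and needs no eye examination before the first dose, a narrow gap that mainly affects crossover after chemotherapy has ended

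*Protocol*

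**What the plan says.** **Entry.** Criterion 18 in Section 5.3 excludes a child with "A history or current evidence of retina vein occlusion (RVO) or central serous retinopathy". The Amendment 4 rationale explains its addition: "This exclusion criteria is standard language for all studies with trametinib and was inadvertently omitted from previous versions of CDRB436G2201". Table 7-1 gives children who start dabrafenib plus trametinib as randomised treatment a screening eye examination.

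**Crossover.** Section 4.1.2.2 has its own, shorter list. The child must still meet the cardiac inclusion criteria, and then: "be willing to follow all contraception guidance, and cannot meet the exclusion criteria for allergy to dabrafenib, trametinib, or their excipients". Measurable disease is waived. Day 1 may be up to 90 days after the first centrally confirmed progression. Assessments follow Table 7-2.

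**Timing.** Section 4.1 states: "Crossover will be allowed during the treatment period or the post-treatment period". Section 4.1.2.2 adds a possible crossover for control children with stable disease after the final PFS analysis, if the results favour the experimental arm.

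**Retinal findings on treatment.** Section 6.3.1.4 says: "Treatment emergent cases of RVO and RPED are to be reported as SAEs". Table 6-19 says: "If RVO diagnosed: Permanently discontinue trametinib and report as SAE".

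**The concern.** A crossover child meets trametinib for the first time, just as a child randomised to it does, but with a weaker eye check. The sponsor regards the retinal exclusion as standard wherever trametinib is given, yet the crossover list omits it, and the crossover schedule looks at the heart beforehand but not at the eye.

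Two things are at stake. First, a child with undiagnosed retinal vein occlusion or central serous retinopathy could start the drug while the protocol is followed to the letter. If occlusion is then found at the first on-drug examination, trametinib must stop permanently. Second, without a recent pre-dose examination it is hard to say whether a retinal finding at Week 5 is new. The rule on serious adverse event reporting turns on the finding being treatment-emergent.

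**Working it through.** **Step 1: the schedules side by side** (row "Ophthalmic examination" against the cardiac rows).

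| Row | Table 7-1, randomised to D+T | Table 7-2, crossover | Table 7-3, chemotherapy |
|---|---|---|---|
| ECG, ECHO before first dose | X | X | X |
| Eye examination before first dose | X | blank | X |
| First eye examination on treatment | Week 5 | Week 5 | Week 5 |
| Later eye examinations | 16, 32, 48, 72+, EoT | 16, 32, 48, 72+, EoT | 16, 32, 48, 56, EoT |
| Eye examination in post-treatment follow-up | none | none | none |

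Section 7.2.2.7 refers back to these tables. Beyond them it allows repeats when clinically warranted and requires a detailed examination if changes are noted or there is a clinical indication. Nothing there obliges an examination before crossover in a child without symptoms.

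**Step 2: age of the last scheduled eye examination at crossover Day 1.** Assumptions: no chemotherapy delay, follow-up visits counted from EoT, and the 90-day limit counted from the date progression is found.

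- Last carboplatin dose: 12 weeks of induction + 7 full maintenance cycles of 6 weeks + 4 = Week 58. EoT is within 30 days, so Week 58 to 58 + 30/7 = 62.3.
- Progression ends chemotherapy and EoT is done then: 0 to 90/7 = 12.9 weeks.
- Progression at the first follow-up visit (16 weeks ± 14 days): 14 weeks to 18 + 12.9 = 30.9 weeks.
- Progression at Week 104: 104 − 62.3 = 41.7 weeks to 104 − 58 + 12.9 = 58.9 weeks.

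Later progression, or crossover with stable disease after the final PFS analysis, can give longer gaps.

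**Step 3: first scheduled examination on trametinib.** Week 5 Day 1 is (5 − 1) × 7 = 28 days after the first dose; with the ± 2 day window, 26 to 30 days.

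**Step 4: how many children.** The control arm is 102/3 = 34. The planned course ends at Week 12 + 8 × 6 = 60. Assume exponential PFS with median m, so F(w) = 1 − 2^(−w/m). The number progressing after Week 60 and by Week 104 is 34 × (F(104) − F(60)):

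- m = 12 months: 34 × (0.749 − 0.549) = 6.8
- m = 24 months: 34 × (0.499 − 0.329) = 5.8
- m = 60 months: 34 × (0.241 − 0.147) = 3.2

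Only the 60-month value has a source in the protocol (about 5 years in unselected patients, Section 2.1). The other two are assumptions for a mutation that the protocol describes as having worse PFS. The results count chances to cross over, not harms.

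**Step 5: controls randomised before criterion 18 existed.** By 28-Feb-2019, "fourteen (14) patients have been randomized in the LGG cohort of CDRB436G2201". The arm split is not given. At 2:1 the expected number of controls is 14/3 = 4.7; if assignment was simple randomisation, the 2.5% and 97.5% points of Binomial(14, 1/3) are 1 and 8.

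**The case against.** The case for leaving the text alone has several parts.

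- **Controls are already examined often.** This stands and sets the scope. For a child who completes chemotherapy, only disease arising after EoT escapes the schedule. For a child who progresses on chemotherapy, the EoT examination can serve as a near-crossover baseline.
- **Section 5.1 bars anyone who meets an exclusion criterion from being offered treatment.** This helps only in part. That sentence governs entry, whereas Section 4.1.2.2 sets a specific shorter list and waives measurable disease. If all criteria still applied, the list would serve no purpose.
- **A known occlusion would stop the investigator anyway.** Starting trametinib would clash with Table 6-19. What remains is the symptom-free, undiagnosed case.
- **The short list is deliberate.** Marrow, renal and hepatic criteria are not re-applied either, and criterion 18 covers mere history, so re-applying it could deny on-study crossover to a child with a progressing tumour. That cost is real. But the protocol gives no reason for dropping the one criterion that it calls standard for trametinib.
- **An added X does not guarantee a retinal examination.** True: Section 7.2.2.7 leaves the components to the investigator. The same holds for the screening examination in Table 7-1, so the fix restores parity and no more.

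Stronger readings are tempting but unsupported. A reader might infer that pre-Amendment 4 controls never had their eyes examined. The documents show only that criterion 18 did not yet exist, and the earlier schedules are not at hand. A reader might also scale up the 4 of 38 children with ocular events in the paediatric trametinib monotherapy study. Those events were of any kind and occurred on the drug, so they do not estimate retinal disease present before crossover. Nor does Section 6.3.1.16.4 show that vincristine makes an EoT retinal examination unreliable: it lists visual change under peripheral neuropathy, not retinal injury.

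**Conclusion.** The point holds in a limited form. Followed exactly, the crossover list and Table 7-2 let a symptom-free child start trametinib without the retinal check that the sponsor requires at entry. Two groups are affected:

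- Children who cross over in post-treatment follow-up, or with stable disease after the final PFS analysis. For progression between the first follow-up visit and Week 104, the last scheduled examination is about 14 to 59 weeks old. Retinal disease that arose after EoT would go unsought until 26 to 30 days into dosing.
- Any controls among the 14 LGG patients randomised before Amendment 4 (about 5 expected at 2:1). They were not formally assessed against criterion 18 at entry, although they may have had eye examinations.

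The ceiling is 34 children; 3 to 7 progress between Weeks 60 and 104 under the assumed medians. The protocol gives no paediatric rate of retinal vein occlusion or central serous retinopathy, so no expected number of affected children can be stated, and none is claimed. This is a low-cost safety correction that should be made. It touches no endpoint, test or efficacy analysis.

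**What to change.** 1. In Section 4.1.2.2, add that a crossover patient must not meet exclusion criterion 18.
2. In Table 7-2, put an X in the Pre-Treatment (Day −28 to −1) cell of the ophthalmic row, to the same standard as the Table 7-1 screening examination. Accept a Table 7-3 examination done within 28 days before crossover Day 1.

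Table 7-3 can stay as it is. With both edits, the last eye examination is at most 28 days old at the first crossover dose.

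The cost is one clause, one table cell, and at most one extra eye examination (occasionally with sedation) for a crossover child without a recent one. A child found to meet criterion 18 would lose on-study crossover, which is the rule that already applies at entry.
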